6.1.3 PRIMARY AND SECONDARY STUDY ENDPOINTS

PRIMARY STUDY ENDPOINT

The capability of PulmoVista 500 for continuous monitoring of ventilation and its changes at different points in time during varying states of regional ventilation, the cross-correlation function (CCF) between global tidal impedance (EIT) waveforms and global tidal volume (ventilator) curves will be evaluated.

SECONDARY STUDY ENDPOINTS

- First secondary endpoint: To assess the capability of PulmoVista 500 to detect changes in regional ventilation by evaluating the cross correlation between impedance waveforms derived from PulmoVista 500 and volume curves derived from ventilator during one-lung-ventilation.
- Assess that changes of tidal volumes induced by ventilator settings can be monitored by the "Trends view"
- Assess that changes of the end-expiratory lung volumes (induced by e.g. PEEP changes, recruitment and suctioning maneuvers) can be monitored by "dELLI trend view"

- Documentation of any safety events related to the use of PulmoVista 500
- Assessing the use specific clinical helpfulness of PulmoVista 500 - clinical helpfulness of PulmoVista 500 is proven if
 - see attachments (chapter 23.1) clinical usability

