6.4.2.2 PATIENTS SCHEDULED FOR ELECTIVE SURGERY WITH OLV

Patients scheduled for elective surgery will receive medical care according to the hospital's established standards. Before anesthesia induction, study team will re-evaluate whether all in- and exclusion criteria are appropriately met (e.g. still intubated). Patients are considered "enrolled" when written informed consent has been obtained and all in- and exclusion criteria are appropriately met.

After arrival in the induction room, patients will be connected to the appropriate monitors for routine patient care. Additionally, patients will be asked to sit up and have the electrode belt of PulmoVista 500 fitted to their thorax according to the IfU. Investigational device is set up and connected to the patient and related devices.

Before and during pre-oxygenation of the patient, study personnel will start and test recording of the data. Anesthesia induction, placement and confirmation of correct placement of the DLT / bronchial blocker will be performed according to the hospital's established standards of care.

In patients who require independent lung ventilation during their surgical procedure, EIT measurements shall be performed during normal (both lungs) and single-lung ventilation after induction of anesthesia before start of surgery. According to standard of care correct positioning of the DLT respectively of the bronchial blocker will be tested by switching between normal ventilation and single-lung ventilation (right and left lung will be tested independently).

During the anesthesia induction, study personnel will note the time of particular events (e.g. start of induction, mask ventilation, intubation, clamping left/right) by using the clock on PulmoVista 500. The physician in charge of the anesthesia will be asked to allow uninterrupted baseline readings of at least 2 minutes after successful intubation and to keep the left and right lumen of the DLT clamped for at least 1 minutes each to ensure stable recording of the data. Each step of the testing of correct placement of the DLT or the bronchial blocker will be marked in PulmoVista 500 before the conduct of this step.

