1.3 DEFINITIONS

The intention-to-treat collective comprises all patients for which both, the impedance waveforms and parallel to them volume waveforms have been generated during ventilation. If one of the two waveforms has not been created or cannot be evaluated, the patient is considered as drop out.

A waveform is not generated if

- a) it has not been recorded correctly, so all the individual values are zero or
- b) there is no complete 1-minute file before the "PRE" marker or behind the "POST" marker available for the statistical calculation of the cross-correlation coefficient.

¹ Teschner E, Imhoff M, Leonhardt S. Electrical Impedance Tomography: The realisation of regional ventilation monitoring. Drägerwerk AG & Co. KGaA 2015; Reference-Nbr 90 66 788;

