3.3 SECUNDARY STUDY OBJECTIVES

3.3.1 Efficacy

- To demonstrate the ability of PulmoVista 500 to display regional ventilation changes, a quantitative evaluation is performed using the cross-correlation coefficient between the impedance waveforms of PulmoVista 500 and the ventilator volume waveforms in the subgroup of OLV patients.
- To evaluate Pulmo Vista 500's monitoring features, it assesses whether changes in tidal volumes induced by ventilation settings are represented by the "main view". For this purpose, the plausibility questionnaire is evaluated.

- Assess that changes of the end-expiratory lung volumes (induced by e.g. PEEP changes, recruitment and suctioning maneuvers) can be monitored by “dEELI trend view”. The plausibility questionnaire is also evaluated for this.
- To evaluate the clinical usefulness of PulmoVista 500, the questionnaire on clinical utility across all patients is evaluated.
- In order to demonstrate the ability of PulmoVista 500 to produce controlled induced regional changes, an evaluation is performed using the OLV subgroup. Three blinded rater evaluate the corresponding waveforms.

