To refute the hypothesis of independence of both waveforms, it has to be shown that the global impedance waveforms (as measured by the PulmoVista 500) and the global volume waveforms (of the EvitaV500 ventilator) correlate significantly (rejection of the null hypothesis "no correlation"). Because 2 experimental steps (before and after each intervention) should be performed in 80 patients, 80 averaged (from the pre- and post-values) cross-correlation coefficients will be obtained in total. If, for technical reasons (for example, incorrectly set markers), there are only pre- or post-values, the averaging in this patient is omitted and only one cross-correlation coefficient is used. From these averaged cross-correlation coefficients, a 95% confidence interval is calculated and a one sample t-test is performed to determine if the mean of the cross-correlation coefficients is significantly different from zero.

The significance level is $\alpha = 0.05$.

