5.6 SECUNDARY ANALYSIS

5.6.1 Efficacy

- To demonstrate the ability of PulmoVista 500 to visualize regional ventilation changes, a quantitative evaluation is performed by calculating the cross-correlation coefficients between the impedance waveforms of PulmoVista 500 and the ventilator volume waveforms of OLV patients. The evaluation is carried out as in the primary analysis.
- In addition, a qualitative evaluation of the regional changes will be carried out. To do so, three blinded raters compare the corresponding sections of all OLV patients independently. Based on the information from the PulmoVista 500 video sequence provided, the raters evaluate which of the two halves of the lung is ventilated. The results are entered patient-related (pseudo-patient number) in the following table by the rater:

Pseudo-Patnr.	Valuation	
1	1	
2	2	
3	0	
4	1	
.	.	

Description of valuation:	0	not assessable
	1	right ventilated / left blocked
	2	left ventilated / right blocked

Tab. 1: Example of table for the qualitative evaluation of the OLV patients and the associated rating

The PulmoVista 500 video sequences to be assessed are created according to a workflow (see Appendix 7.3 Workflow for the creation of OLV videos) and made available to the raters. The pseudo-patient numbers are randomly generated by lot. These three tables of the raters will be merged into the KKS. A decision is considered positive or negative if at least two raters have come to the same result. In the opinion of one or more raters, is it not possible to judge the waveform (Code 0), the following assignment applies:

1x not evaluable & 2x same decision -> clear assignment in the table,
 1x not assessable & unequal decision of the remaining 2 raters -> drop out,
 2x or 3x not evaluable -> drop out.

A 2x2 Table will be created in the following form from the 3 tables of the raters (one of each rater):

Reference	Evaluation of the raters (with information provided by PulmoVista 500)	
	right ventilated / left blocked	left ventilated / right blocked
right ventilated / left blocked	a	b
left ventilated / right blocked	c	d

Tab. 2: Table for the accordance of rater and reality of the OLV patients

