7 APPENDIX

7.1 REFERENCE VALUES OF LABORATORY PARAMETERS

[figure not shown]
Omitted

7.2 WORKFLOW FOR DETERMINING THE TIME RANGES USED TO CALCULATE THE CROSS CORRELATION BETWEEN THE GLOBAL IMPEDANCE WAVEFORM (PULMOVISTA 500) AND THE VOLUMETRIC WAVEFORM (EVITA V500).

Workflow for determining the time ranges used to calculate the cross correlation between the global impedance waveform (PULMO VISTA 500) and the volume waveform (EVITA V500)

[figure not shown]
Step Description

- 1 Open EIT Data Analysis Tool SW 6.1
- 2 Use the **Load** button to load the first file in the series containing the intervention to be evaluated; the beginning and the type of intervention are marked by an event marker (see example below)
- 3 Use the button **Sequence to ...** to load the last file of the series containing the intervention to be evaluated
- 4 Record the total length of the loaded files (time scale below ROI 4)

[figure not shown]
5 Select the files (1 min each) that lie directly before (1) or after (2) the intervention, in which a uniform impedance waveform, and in particular no artifacts, can be seen and in which no parts of the intervention itself are contained.

Example: series of 10 files per 1 min, in which the interventions took place between min 3 and 4.

[figure not shown]

6 Place cursor in the area of file 1 (exact position does not matter, in this example within the third minute)

- 7 Use the buttons **Display ...**, **Time scale** to set the time scale to 60 sec

- 8 Use the button **File ..., save as ASC** to convert the selected file 1 as ASCII file
(the created ASC file is saved in the same directory with the same file name as the selected EIT file, and a two-digit, incremental counter is added to the file name)
- 9 Use the Buttons **Display ...**, **Time scale** to increase the time scale so that the recorded total length is displayed again.
- 10 Place cursor in the area of file 2 (exact position does not matter, in this example within the 5th minute)
- 11 Use the buttons **Display ...**, **Time scale** to set the time scale to 60 sec

- 12 Use the button **File ..., Save as ASC** to convert the selected file 2 as ASCII file
- 13 Now open the two generated ASC files with the statistical evaluation software
- 14 In the area below the line (Image; Time; Global;), Determine the cross-correlation between column C (Global) and column N (~ Volume [ml]).

97	A	B	C	D	E	F	G	H	I	J	K	L	M	N

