7.3 WORKFLOW FOR THE CREATION OF OLV VIDEOS

This workflow describes the creation of the video sequences which are used to assess the capability of PULMO VISTA 500 to monitor regional changes during mechanical ventilation within the OLV-subgroup.

Software:

- Dräger EIT Simulation Tool
- Camtasia Recorder 8
- Camtasia Studio 8

Workflow:

1. Identify the acquisition dates and the patient/site IDs of all OLV patients
2. Identify relevant markers which are set prior and post the induction of one lung ventilation
 - a. document time-stamp of each marker
3. Load EIT-data into *Dräger EIT Simulation Tool*
 - a. Select the “Folder” which contains the acquisition date
 - b. Select the “Subfolder” which contains the relevant patient ID (xx_yyy)
 - c. Select the start-“File” which includes the relating “PRE-Marker”
 - d. Select the “Sequence to file” which includes the relating “POST-Marker”
4. Start *Camtasia Recorder 8*
5. Adjust the recording window according to the size of the “Main”-view
6. Start the simulation within *Dräger EIT Simulation Tool*
7. Start the recording
8. After the simulation has completed one entire loop of simulation, stop the recording
9. Save the recorded video file (use site and patient ID, as well as date of recording) for the definition of the file name
10. Load recorded video file into *Camtasia Studio 8*
11. Crop video sequence according to the previously identified time-stamps of the pre and post markers (the video sequence now contains only the EIT information between the two markers)
12. Process the final video sequence as MP4-file
13. Save the MP4-file containing the respective site and patient ID as well as the date of video processing.

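### The one-lung-ventilation cross-correlation is averaged with a minute recorded before one-lung ventilation, so it ordinarily holds at most half one-lung data

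*SAP*

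**What the plan says.** - **Endpoint.** Protocol 6.1.3 (and the synopsis) ties the first secondary endpoint to a ventilation phase. It is the cross-correlation of impedance waveforms with "volume curves derived from ventilator during one-lung-ventilation".
- **SAP restatement.** SAP 3.3.1 ties it to a patient group instead: "the ventilator volume waveforms in the subgroup of OLV patients".
- **Method.** SAP 5.6.1 gives no OLV-specific rule: "The evaluation is carried out as in the primary analysis".
- **Primary method.** SAP 5.5 yields one mean per patient: "80 averaged (from the pre- and post-values) cross-correlation coefficients will be obtained in total". If only one of the two values exists for technical reasons, that value is used alone. The mean over patients gets a 95% confidence interval and a one-sample t-test against zero.
- **Windows.** Under SAP 1.3, a waveform counts as not generated if "there is no complete 1-minute file before the" PRE marker or behind the POST marker. Appendix 7.2, step 5, selects 1-minute files directly before and after the intervention, "in which no parts of the intervention itself are contained". Step 14 correlates the Global column with volume. Step 15 calculates each file separately, then averages.
- **Markers in OLV patients.** Appendix 7.3, step 2, places them before and after the induction of OLV. After cropping (step 11), "the video sequence now contains only the EIT information between the two markers", and from these clips the raters judge which lung is ventilated.
- **Length of the one-lung phases.** Protocol 6.4.2.2 has the anaesthesia physician asked "to keep the left and right lumen of the DLT clamped for at least 1 minutes each".

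**The concern.** The protocol asks how well the two signals agree while one lung is ventilated. The SAP instead reports a per-patient average over two windows chosen to lie outside the marked interval, and the first of these ordinarily precedes OLV. The average does not estimate the quantity the protocol names. If agreement fell during OLV, the reported figure would hide part of the fall, or all of it if the POST file is not one-lung data. The planned test gives no protection, because good agreement before induction can be enough to reject a zero mean.

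The SAP also presents this CCF as evidence that the device displays regional changes. A correlation built on the Global signal cannot show that.

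**Working it through.** **1. The plan's own figures.** The documents state no one-lung share, so there is none to reproduce. The CCF sample size in protocol 7.1 does reproduce: difference 0.1 and SD 0.25 give d = 0.1/0.25 = 0.4. A two-sided one-sample t-test at alpha 0.05 and power 0.9 needs n = 68 (power 0.902), and 68/0.85 = 80. The OLV subgroup (22, enrolled as 25) was sized on a proportion, so no planned precision exists for its CCF. I borrow the SD of 0.25 and n = 22 for step 4.

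**2. One-lung share.** Share = one-lung windows / averaged windows.

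- PRE file: before induction, so ordinarily two-lung. It contributes 0.
- POST file: contributes 1 if OLV runs for a whole file after POST, otherwise 0.
- Share = (0 + 1)/2 = 50% at most, or (0 + 0)/2 = 0%.

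**3. Can the POST file be one-lung?** The raters must see the ventilated side between the markers, so some OLV lies before POST, in the interval the CCF omits. Only what remains after POST can fill the POST file. If a clamp lasts the requested minimum of 1 minute and part of it precedes POST, less than 1 minute remains and no complete 1-minute file fits. For longer phases, assume file boundaries fall at random and let L be the minutes of OLV left after POST. For L between 1 and 2, P(complete file fits) = L − 1:

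| L (min) | P |
|---|---|
| 1.0 | 0 |
| 1.5 | 0.5 |
| 2.0 | 1 |

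Actual phase lengths are not in the documents, and the 1-minute request is worded for the double-lumen tube only.

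**4. Dilution.** Reported value = (CCF before + CCF during)/2 when the POST file is one-lung. All CCF values here are assumed.

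- 0.95 before and 0.60 during: (0.95 + 0.60)/2 = 0.775. The true fall of 0.35 shows as 0.95 − 0.775 = 0.175. If the POST file is two-lung with the same CCF as before, the report shows 0.95.
- 0.80 to 0.95 before and 0 during: averages 0.80/2 = 0.40 and 0.95/2 = 0.475. With SD 0.25 for the averaged value and n = 22, the standard error is 0.25/√22 = 0.0533. The expected ratios are 0.40/0.0533 = 7.5 and 0.475/0.0533 = 8.9, against a critical t of 2.08 on 21 df. Power exceeds 0.999.

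**5. Regional content.** In the sample export in Appendix 7.2, the line for image 7205 gives Local 1 to 4 as 282.248, 1402.365, 1634.344 and 161.750. They sum to 3480.71, the Global value to two decimals. A shift between these regions that leaves the sum unchanged does not alter Global.

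**The case against.** **The endpoint is measured after all.** Induction most naturally means onset. POST then falls while OLV is running, and the minute behind it is one-lung data. Step 15 computes that coefficient separately before averaging, so it exists and is merely pooled. This largely stands. A reader might infer that the endpoint is not measured at all, but the documents do not support that: no passage says POST marks the end of OLV. What remains is the averaging, and the lack of any rule ensuring a whole one-lung file after POST.

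**The PRE file need not be two-lung.** Both sides are clamped, and the SAP does not say which clamp supplies the marker pair. If one clamp followed the other directly and the second pair were used, PRE could hold OLV of the other side. This stands, so an unqualified statement that PRE is always two-lung, or that the share is exactly 50% or 0%, goes too far.

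**Single values are not averaged.** Under SAP 5.5 a patient with only a post-value could contribute wholly one-lung data. This also stands, although SAP 1.3(b) appears to make such a patient a drop-out.

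**Regional detection is tested elsewhere.** Protocol 7.2 tests it with a 2x2 table. SAP 5.6.1 uses three blinded raters and reports success rate, sensitivity, specificity and confidence intervals. It would therefore be wrong to infer that regional detection goes unassessed or that a new left/right impedance endpoint is required. The table does not, however, supply the CCF during OLV.

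**Evidence is limited.** The workflow figures are not reproduced in the text available and may show marker placement. The clip-cropping step concerns videos; the CCF windows are set in SAP 1.3, 5.5 and Appendix 7.2.

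**Conclusion.** The mismatch is real. Where both values exist, the SAP's OLV coefficient is ordinarily at most half one-lung data and may contain none. It does not estimate the protocol's CCF during OLV. Poor agreement in that phase would be at least halved in the report, and the test against zero could reject with no agreement there at all.

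The bound rests on PRE preceding OLV, which follows from the marker definition in Appendix 7.3, and on equal-weight averaging. It does not cover single-value patients or a second-clamp marker pair. The CCF values and the random file offset are assumptions. The documents give no observed OLV coefficient, so they do not show that agreement actually falls.

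This should be fixed before analysis but is not critical to the trial: the endpoint is secondary, protocol 7.3 sets no pass/fail criterion, and the primary analysis is unaffected.

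**What to change.** In SAP 5.6.1, replace the reference to the primary method for OLV patients with a rule of its own:

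- Compute the CCF on windows cut by event markers and lying wholly inside the one-lung phase, for each side where available, rather than on whole-minute files.
- Do not average it with the pre-induction value. Report the two-lung CCF, the one-lung CCF and their within-patient difference, with confidence intervals.
- State which markers define the start and end of each phase and which clamp they belong to. State the shortest window accepted, and report how many patients lack one.
- Reconcile the single-value rule in SAP 5.5 with the drop-out rule in SAP 1.3(b).
- In SAP 3.3.1 and 5.6.1, rest the claim of regional detection on the rater 2x2 table and not on this CCF.

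The cost is SAP wording and re-cutting of existing recordings. Event times are already to be noted on the device clock and clamp steps marked in the device (protocol 6.4.2.2), so no new data are needed. The price is somewhat shorter windows, hence somewhat less stable coefficients per patient.

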7.4 PLANNED TABLES (EXEMPLARY)

nn

7.5 PLANNED DATA LISTS (EXEMPLARY)

nn

7.6 PLANNED FIGURES (EXEMPLARY)

nn

7.7 EVALUATION ROUTINES

Example of the calculation of the cross correlation coefficients: (in the example the maximum cross-correlation coefficient is **CCF=0.984** by a lag-shift of 8)

```
GET DATA
  /TYPE=XLSX
  /FILE='U:\Verz_Studien\PULMOVISTA\XXX\XXX_prae.xlsx'
  /SHEET=name 'Tabelle1'
  /CELLRANGE=FULL
  /READNAMES=ON
  /DATATYPEMIN PERCENTAGE=95.0
  /HIDDEN IGNORE=YES.
EXECUTE.
DATASET NAME DataSet1 WINDOW=FRONT.

SAVE TRANSLATE OUTFILE='U:\Verz_Studien\PULMOVISTA\XXX\XXX_prae.xlsx'
  /TYPE=XLS
  /VERSION=12
  /MAP
  /FIELDNAMES VALUE=NAMES
  /CELLS=VALUES
  /REPLACE.

Data written to U:\Verz_Studien\PULMOVISTA\XXX\XXX_prae.xlsx'.
4 variables and 3000 cases written to range: SPSS.
Variable: Image          Type: Number    Width:  5    Dec: 0
Variable: Time           Type: Number    Width: 12    Dec:10
Variable: Global          Type: Number    Width: 18    Dec:13
Variable: RTDVol.mL       Type: Number    Width: 19    Dec:15

SAVE OUTFILE='U:\Verz_Studien\PULMOVISTA\XXX\XXX_prae.sav'
  /COMPRESSED.
DATASET ACTIVATE DataSet1.
CCF
  /VARIABLES=Global RTDVol.mL
  /NOLOG /MXCROSS 15.
```

CCF

[DataSet1] U:\Verz_Studien\PULMOVISTA\XXX\XXX_prae.sav

Model Description

Model Name	MOD_1	
Series Name	1	Global
	2	RTDVol.mL RTD: Vol. [mL]
Transformation	None	
Non-Seasonal Differencing	0	
Seasonal Differencing	0	
Length of Seasonal Period	No periodicity	
Range of Lags	From	-15
	To	15
Display and Plot	All lags	

Applying the model specifications from MOD_1

Case Processing Summary

Series Length	3000
Number of Excluded Cases	User-Missing Value
Due to	System-Missing Value
Number of Valid Cases	3000
Number of Computable Zero-Order Correlations After	3000
Differencing	

Global with RTDVol.mL RTD: Vol. [mL]

Cross Correlations

Series Pair: Global with RTDVol.mL

RTD: Vol. [mL]

Cross		
Lag	Correlation	Std. Error ^a
-15	,687	,018
-14	,710	,018
-13	,732	,018
-12	,754	,018
-11	,774	,018
-10	,794	,018
-9	,813	,018
-8	,831	,018
-7	,848	,018
-6	,865	,018
-5	,880	,018
-4	,895	,018
-3	,909	,018
-2	,921	,018
-1	,933	,018
0	,943	,018
1	,953	,018
2	,961	,018
3	,968	,018
4	,974	,018
5	,978	,018
6	,981	,018
7	,983	,018
8	,984	,018
9	,983	,018
10	,981	,018
11	,977	,018
12	,972	,018
13	,966	,018
14	,958	,018
15	,949	,018

a. Based on the assumption that the series are not cross correlated and that one of the series is white noise.

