7 STATISTICAL CONSIDERATIONS

7.1 SAMPLE SIZE, DROP-OUT-RATES, LEVEL OF SIGNIFICANCE AND POWER OF THE CLINICAL INVESTIGATION

Primary Endpoint (Efficacy)

Based on former porcine trials⁷ with PulmoVista 500 and data from clinical studies with other EIT devices the sample size was calculated using the program G*Power 3.1.9.2.

An α -error of $p = 0.05$ and a power = 0.9 in a two-sided testing resulted in a sample size of 68 patients. With this sample size a difference of 0.1 of the mean cross-correlation coefficient shall be detected, i.e. the true value of a calculated mean of 0.8 will not be smaller than 0.7 and not be larger than 0.9 with the given p-value and power under the assumption of a standard deviation of less than .25.

Accounting for 15 % potential drop-outs 80 patients shall be enrolled in the study.

Secondary Endpoint (Efficacy)

Based on former porcine trials with PulmoVista 500 and data from clinical studies with other EIT devices the sample size was calculated using the program G*Power 3.1.9.2. An α -error of $p = 0.05$ and a power = 0.9 in a two-sided testing resulted in a sample size of 22 patients. With this sample size a difference of 0.1 of the proportion between reference and investigated variable shall be detected.

Accounting for 15 % potential drop-outs 25 patients shall be enrolled in this subgroup of the study.

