5.5 PRIMARY ANALYSIS

The basic data for the analysis is recorded in a database. The ventilation data for both waveforms- the global impedance waveforms and the volume waveforms- are stored for each patient in a cloud and prepared using a statistical analysis algorithm (see Appendix 7.2 Workflow for determining the time ranges used to calculate the cross correlation between the global impedance waveform (PulmoVista 500) and the volumetric waveform (Evita V500)).

The two EXCEL tables per patient contain the two waveforms to be compared (Appendix 7.2, Section 14, Columns A, B, C and N). From this, two cross-correlation coefficients per patient were calculated. The cross-correlation coefficients are a measure of the relationship between the two waveforms.

Figure 1 shows a section of both waveforms unstandardized. The numbers and diagrams are examples from the study „Assessment of the capability of PulmoVista 500 to

continuously monitor regional ventilation distribution and its changes over time",
Investigation reference number PulmoVista 500-30022.

[figure not shown]

Fig. 1: PulmoVista 500 Impedance Waveform (Global- blue) and Reference Volume Waveform (RTD_Vol_mL- green) unstandardized over time

If you standardize both waveforms, you get the following figure:

[figure not shown]

Fig. 2: PulmoVista 500 Impedance Waveform (Global- blue) and Reference Volume Waveform (RTD_Vol_mL- green) standardized over time

Figure 2 shows a slight time shift of the waveforms to each other.

In this example there is e.g. a correlation coefficient (Pearson) of 0.871 for the waveforms. Taking into account the shift (here Lag = 10: Shift from one curve to the other by 10 measuring times in both directions from 0) it results in a cross-correlation coefficient of 0.995.

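### The primary coefficient is a maximum over 31 lags, so its mean is above zero even for unrelated curves and the t-test against zero does not keep its 5% level

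*SAP*

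**What the plan says.** SAP 5.5 explains by example that the two curves are shifted against each other before the coefficient is read off. A Pearson correlation of 0.871 becomes 0.995 once the shift is allowed for ("here Lag = 10: Shift from one curve to the other by 10 measuring times"). The routine in SAP 7.7 requests 15 lags in each direction, 31 in all, and reports the top of the list: "in the example the maximum cross-correlation coefficient is" 0.984 at lag 8. The same table gives 0.943 at lag 0.

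The pre and post coefficients are averaged to one value per patient. Then "a one sample t-test is performed to determine if the mean of the cross-correlation coefficients is significantly different from zero", at a significance level of 0.05. SAP 5.5 presents rejection as refuting independence of the two curves. SAP 5.6.1 applies the same evaluation to the one-lung-ventilation subgroup.

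Neither section states a rule for choosing the lag, a maximum shift in seconds, or an allowance for having searched over lags.

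**The concern.** A correlation at one lag chosen in advance averages zero when two curves are unrelated. The largest of 31 such correlations does not: it picks the most favourable alignment in each file, so its expectation is positive. A t-test of its mean against zero then tests something that is false even when the device signal carries no information on volume.

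This matters because the test is the only formal decision in the plan. Protocol 7.2 lets rejection stand for the device being valuable for long-term monitoring, Protocol 7.3 defines no pass/fail criterion, and Protocol 3.2 expects the data to support authorization in other countries. A test that unrelated curves would also pass adds little to that case.

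**Working it through.** **The plan's own figure first.** Protocol 7.1 states "a power = 0.9 in a two-sided testing resulted in a sample size of 68 patients", for a difference of 0.1 "under the assumption of a standard deviation of less than .25". The standardised difference is 0.1/0.25 = 0.4. The exact one-sample t-test at two-sided 0.05 needs n = 68 (power 0.902), and 68/0.85 = 80. Both figures reproduce, so the sample size is not in dispute.

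**Frame rate and window.** In the SAP 7.2 export, 13 steps run from 0.51702906 to 0.51703659. Read as fractions of a day, the step is (0.51703659 − 0.51702906)/13 × 86,400 = 0.050 s, or 20 Hz, which is 1,200 rows per 1-minute file. The SAP 7.7 example has "4 variables and 3000 cases written". If that is a 1-minute file, the rate is 3000/60 = 50 Hz. So ±15 samples is ±15/20 = ±0.75 s in the first case and ±15/50 = ±0.30 s in the second.

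**Simplest null case.** For white noise, one lag has standard error 1/√N; with N = 3000 this is 0.018, the value printed in SAP 7.7, whose footnote confirms the single-lag assumption. The expected maximum of 31 independent standard normals is 2.06, so the expected maximum coefficient is
- 2.06/√3000 = 0.038 for 3,000 rows,
- 2.06/√1200 = 0.059 for 1,200 rows.

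**Simulation of unrelated pairs.** Assumptions: 60 s files, two files averaged per patient, n = 68, 31 lags, signed maximum, two-sided t-test against 0. The periodic curves have two harmonics and independent rates of 12 to 25/min.

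| Curves | Rate | Mean of maximum | SD of maximum | Rejects, maximum | Rejects, lag 0 |
|---|---|---|---|---|---|
| White noise | 50 Hz | 0.038 | 0.009 | 100% | 5% |
| White noise | 20 Hz | 0.060 | 0.014 | 100% | 5% |
| AR(1), 0.95 | 50 Hz | 0.039 | 0.076 | 100% | 5% |
| AR(1), 0.95 | 20 Hz | 0.065 | 0.116 | 100% | 5% |
| Periodic | 50 Hz | 0.049 | 0.183 | 92% | 5% |
| Periodic | 20 Hz | 0.104 | 0.196 | 100% | 5% |

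The lag-0 control was centred at its simulated mean, so about 5% is expected there; it shows that the t-test itself behaves with these distributions. Before centring, the lag-0 means were −0.0002 to 0.005.

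The rates can be checked by hand: t ≈ mean × √(2 × 68)/SD. For periodic curves this is 0.104 × 11.66/0.196 = 6.2 at 20 Hz and 0.049 × 11.66/0.183 = 3.1 at 50 Hz, against a critical value of about 2.0.

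With ramp-and-decay breath shapes instead, the mean maximum was 0.10 at 20 Hz (100% rejection) and 0.04 at 50 Hz (81% to 91%).

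**At the planned values.** SE = 0.25/√68 = 0.030. If the mean is 0.8, t = 0.8/0.0303 = 26 against zero and 0.7/0.0303 = 23 against a null mean of 0.10.

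**The case against.** The strongest reply is that the decision would not change: with t about 26 or 23, the planned mean of 0.8 is far from either reference. Zero is also a weak reference with or without a lag search. Both points stand. They limit the harm but do not restore the 5% level or the meaning attached to rejection.

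Second, the maximum appears in worked examples and is not written as a rule. If the lag were chosen by largest absolute value with the sign kept, the simulated rejection rate would be about 4% to 7% at 50 Hz. At 20 Hz it would be about 5% for white noise and AR(1) series, but 14% for periodic curves at unrelated rates. The signed maximum is the natural reading of SAP 7.7, but the plan should say so.

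Third, shifting the curves to remove a technical delay is legitimate. That supports a stated, bounded shift, not a free choice per file tested against zero.

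A reader might also infer more than the documents support:
- *That SAP 5.5 (±10) and SAP 7.7 (±15) conflict.* The 10 belongs to a worked example and may be the shift found or the range searched. In the SAP 7.7 table the peak is at lag 8, so both windows give 0.984.
- *That coefficients are not comparable between recordings because frame rates differ.* SAP 5.5 takes its example from study 30022, which a footnote to Protocol 7.2 identifies as an animal study. The 3,000-row example uses a similar volume label, while the SAP 7.2 export uses another. The 3,000 rows may therefore be animal data, and varying frame rates within this trial are not shown.
- *That the window alone moves the coefficient by about 0.4.* Simulated means of 0.31 (50 Hz) and 0.73 (20 Hz) arise only if both curves share one breathing rate with uniformly random timing. Those are not unrelated curves, and nothing in the documents suggests delays spread over a whole breath.

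**Conclusion.** The point holds. As exemplified in SAP 7.7, the primary statistic has a null mean of about 0.04 to 0.10 for unrelated breathing curves. The t-test against zero would reject in about 80% to 100% of trials with 68 patients, at a nominal 5%. Zero is the wrong null value for this statistic.

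The sizes rest on assumed breath shapes, rates of 12 to 25/min and the signed-maximum reading; the upward direction did not depend on the curve shapes tried.

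A reader might infer that a positive trial result would be false. The documents do not support that: near a true mean of 0.8 the null hypothesis is rejected under either reference. What is lost is the evidential value of the p-value, and the reported mean and confidence interval are shifted upward. The null shift of 0.04 to 0.10 should not be subtracted from a high observed mean. In the SAP 7.7 example the gain over lag 0 is 0.984 − 0.943 = 0.041, and part of that may be proper alignment.

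**What to change.** In SAP 5.5 and 7.7:
1. State the lag-selection rule, including whether the maximum is signed.
2. Set one maximum shift in seconds, justified by the technical delay between the two signals, and convert it to samples from the frame rate of the recording.
3. Report the chosen lag and the zero-lag correlation beside each coefficient.
4. Replace zero as the reference with the null mean from the same routine run on mismatched pairs (impedance curve of one patient, volume curve of another). Alternatively, keep the test against zero but apply it to the coefficient at a lag fixed in advance.
5. Apply the same rule to the one-lung-ventilation analysis in SAP 5.6.1.

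Optionally, show the lower 95% limit beside the 0.7 of Protocol 7.1. This would be descriptive: Protocol 7.1 uses 0.7 for planning only, and Protocol 7.3 sets no pass/fail criterion.

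The cost is a little more analysis work and a slightly lower mean coefficient. No new data are needed and the sample size does not change.
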